The PTNS treatment and sham have no recognised significant adverse effects. However, at each weekly visit each patient will be asked if they have suffered any side effects or adverse effects of the treatment. These will be documented and in the study database and reported to the data monitoring committee prior to each meeting with them.

Adverse events leading to withdrawal

Serious adverse events

Clinical laboratory evaluations

SUBGROUP ANALYSES

Definition of outcome measure

Definition of subgroups

Primary outcome –

Sex (male vs. female)

FI severity ($<$ or \geq 7 episodes/wk)

Secondary outcomes –

age (<40 years, 40 to 60 years, 60+ years),

Sample size justification for the subgroup analysis

None

Descriptive analysis for subgroups

Method of analysis

An interaction term will be defined by multiplying the sub group dummy variables by the treatment assignment variable. For age, a global test of the two interaction terms will be performed using a likelihood ratio test.

AMENDMENTS TO VERSION 1.0

The pre-planned subgroup analysis ‘urge versus passive FI episodes’ had been inadvertently left out of version 1.0.

- Further, the sub-group analyses were to be conducted only on the primary outcome and not on the secondary outcomes as previously written.
- The Stata code listed in appendix 14(a) was refined during the analysis to correctly handle patients with fewer than 7 days of bowel diary data and the new code has replaced that previously in 14(a). The code to define stool consistency outcomes was not included in version 1.0 and was developed during the analysis.
- The listing of variables used in the multilevel multiple imputations was updated during the analysis to include more detail and also the imputation model for the four binary outcomes (primary (\geq 50% reduction in FI) and three secondary (\geq 25%, \geq 75%, 100%)).

REFERENCES

Kahan BC & Morris TP. Analysis of multicentre trials with continuous outcomes: when and how should we account for centre effects? *Statist. Med* 2013, 32 1136–1149

APPENDICES

Stata code for creating outcome variables

*** Bowel diary data

```
forvalues i = 1(1)14 {
replace Q3_`i' = "" if Q3_`i' == "."
encode Q3_`i', generate(x)
drop Q3_`i'
rename x Q3_`i'
recode Q3_`i' (1=0) (2=1)
label variable Q3_`i' YN

replace Q4a_`i'="" if Q4a_`i' == "."

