encode Q4a_`i', generate(x)
drop Q4a_`i'
rename x Q4a_`i'
recode Q4a_`i' (1=0) (2=1)
label variable Q4a_`i' YN

replace Q4b_`i'="" if Q4b_`i' == "."
encode Q4b_`i', generate(x)
drop Q4b_`i'
recode x Q4b_`i'
recode Q4b_`i' (1=0) (2=1)
label variable Q4b_`i' YN

replace Q5_`i'="" if Q5_`i' == "."
encode Q5_`i', generate(x)
drop Q5_`i'
recode x Q5_`i'
recode Q5_`i' (1=0) (2=1)
label variable Q5_`i' YN

generate x=real(Q1_`i')
drop Q1_`i'
recode x Q1_`i'
generate x=real(Q2a_`i')
drop Q2a_`i'
recode x Q2a_`i'
generate x=real(Q2b_`i')
drop Q2b_`i'
recode x Q2b_`i'

encode Q6_`i', generate(x)
drop Q6_`i'
recode x Q6_`i'
recode Q6_`i' (1=.) (6=0) (5=1) (4=2)
label variable Q6_`i' consist
```

```

}
sort PIN
compress

egen controlled = rowtotal(Q1_1 Q1_2 Q1_3 Q1_4 Q1_5 Q1_6 Q1_7 Q1_8
Q1_9 Q1_10 Q1_11 Q1_12 Q1_13 Q1_14), missing
egen uncontrolled_a = rowtotal(Q2a_1 Q2a_2 Q2a_3 Q2a_4 Q2a_5 Q2a_6
Q2a_7 Q2a_8 Q2a_9 Q2a_10 Q2a_11 Q2a_12 Q2a_13 Q2a_14), missing
egen uncontrolled_b = rowtotal(Q2b_1 Q2b_2 Q2b_3 Q2b_4 Q2b_5 Q2b_6
Q2b_7 Q2b_8 Q2b_9 Q2b_10 Q2b_11 Q2b_12 Q2b_13 Q2b_14), missing

egen staining = rowtotal(Q3_1 Q3_2 Q3_3 Q3_4 Q3_5 Q3_6 Q3_7 Q3_8 Q3_9
Q3_10 Q3_11 Q3_12 Q3_13 Q3_14), missing
egen pads = rowtotal(Q4a_1 Q4a_2 Q4a_3 Q4a_4 Q4a_5 Q4a_6 Q4a_7 Q4a_8
Q4a_9 Q4a_10 Q4a_11 Q4a_12 Q4a_13 Q4a_14), missing
egen enema = rowtotal(Q4b_1 Q4b_2 Q4b_3 Q4b_4 Q4b_5 Q4b_6 Q4b_7 Q4b_8
Q4b_9 Q4b_10 Q4b_11 Q4b_12 Q4b_13 Q4b_14), missing
egen social = rowtotal(Q5_1 Q5_2 Q5_3 Q5_4 Q5_5 Q5_6 Q5_7 Q5_8 Q5_9
Q5_10 Q5_11 Q5_12 Q5_13 Q5_14), missing
egen stool = rowtotal(Q6_1 Q6_2 Q6_3 Q6_4 Q6_5 Q6_6 Q6_7 Q6_8 Q6_9
Q6_10 Q6_11 Q6_12 Q6_13 Q6_14), missing

egen m_unc_a = rowmiss(Q2a_1 Q2a_2 Q2a_3 Q2a_4 Q2a_5 Q2a_6 Q2a_7)
egen m_unc_b = rowmiss(Q2b_1 Q2b_2 Q2b_3 Q2b_4 Q2b_5 Q2b_6 Q2b_7)

generate FI_episodes = uncontrolled_a + uncontrolled_b
generate FI_epi_pw = FI_episodes/2

```

*** primary outcome

```

generate Responder_50 = 1 if FI_epi_pw2/FI_epi_pw0<=.5
replace Responder_50 = 0 if FI_epi_pw2/FI_epi_pw0>.5 &
!missing(FI_epi_pw2) & !missing(FI_epi_pw0)

```

*** binary secondary outcomes: 25%, 75%, 100% improvement

```

generate Responder_25 = 1 if FI_epi_pw2/FI_epi_pw0<=.75
replace Responder_25 = 0 if FI_epi_pw2/FI_epi_pw0>.75 &
!missing(FI_epi_pw2) & !missing(FI_epi_pw0)

```

```

generate Responder_75 = 1 if FI_epi_pw2/FI_epi_pw0<=.25
replace Responder_75 = 0 if FI_epi_pw2/FI_epi_pw0>.25 &
!missing(FI_epi_pw2) & !missing(FI_epi_pw0)

```

```

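### The appendix code for the stool-consistency score counts missing diary days as real scores and does not fix which answer gets which score

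*SAP*

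**What the plan says.** All of the relevant text is in the SAP.

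- **Status of the code.** Amendments to version 1.0: "The code to define stool consistency outcomes was not included in version 1.0 and was developed during the analysis". Stool consistency is absent from the outcome lists, the secondary analysis section and the imputation table.
- **Creating the codes.** In the appendix of Stata code for outcome variables, the bowel-diary loop turns each day's Q6 text into numbers with "encode Q6_`i', generate(x". No label name and no text-to-number map are given. The yes/no items go through the same temporary variable first, beginning with "encode Q3_`i', generate(x", and are then set to 0/1, as in "recode Q3_`i' (1=0) (2=1".
- **Scoring.** "recode Q6_`i' (1=.) (6=0) (5=1) (4=2". Codes 2 and 3 have no rule.
- **Cleaning.** For Q3, Q4a, Q4b and Q5, a line before the encode turns '.' into an empty string. No such line is printed for Q6.
- **Summary.** "egen stool = rowtotal(Q6_1 Q6_2 Q6_3 Q6_4 Q6_5 Q6_6 Q6_7 Q6_8 Q6_9", continuing to day 14, with the `missing` option.
- **Comparison.** The gastrointestinal quality-of-life and St Mark's totals are set to missing if any item is missing. No equivalent step is printed for Q6.

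**The concern.** A consistency score should describe the form of the stools that were recorded. It should not depend on how many days the patient filled in, or on the order in which software met the answer texts. The printed code is open to both. A patient who completes the baseline diary fully and the post-treatment diary partly would show a change in `stool` with no change in stool form. If completeness differs between arms, so would the score. The SAP also does not list the Q6 answers or say which end of the scale is loose or firm, so a second analyst could not confirm that the scores follow the intended order. Since this code is the outcome's only definition, nothing else in the document corrects it.

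**Working it through.** No figure for this score is stated in the SAP, so the check is a trace of the code. For several items, Q6 included, a `recode` is printed where Q3 has a `rename`. I read it as a rename and do not count it as a finding.

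**1. The recode rule.** Stata's `recode` leaves unlisted values unchanged:

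| code | 1 | 2 | 3 | 4 | 5 | 6 |
|---|---|---|---|---|---|---|
| score | missing | 2 | 3 | 2 | 1 | 0 |

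**2. Which text holds which code.** Without a `label()` option, `encode` names the value label after the new variable, here `x`. If that label already exists, it is reused and extended. No label is dropped in the printed code. Two readings follow.

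*Shared label (the code as printed).* Assume the yes/no items share two texts, which hold codes 1 and 2. Q6 texts then start at code 3.
- '.' plus three answers on the first encoded day: '.' sorts first and takes 3, and the answers take 4, 5 and 6. The scores are '.' = 3 and answers = 2, 1, 0. The rule that sets 1 to missing does not catch '.'.
- Four answers and no '.': codes 3, 4, 5, 6 give scores 3, 2, 1, 0, a clean reversed scale.
- '.' plus five answers: the last two take codes 7 and 8 and pass through unscored.

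*Fresh label for each variable.* With '.' plus five answers, '.' takes 1 and becomes missing. The answers take 2 to 6 and score 2, 3, 2, 1, 0, so the answers at codes 2 and 4 share score 2.

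**3. The sum.** With the `missing` option, `rowtotal` returns missing only when all 14 days are missing. Otherwise a missing day adds 0.
- 14 days at score 1: 14 × 1 = 14.
- 7 days at score 1 and 7 missing: 7 × 1 + 7 × 0 = 7.
- The same half-complete diary, if the 7 days are '.' scored 3: 7 × 1 + 7 × 3 = 28, which equals 14 complete days at score 2 (14 × 2 = 28).
- A diary entered wholly as '.' and scored 3: 14 × 3 = 42, above the 28 that the listed scores can reach.

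**4. Under a mean over recorded days.** 14/14 = 1 and 7/7 = 1, so the two diaries at score 1 agree whatever their completeness.

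Step 3's first two lines hold under either label reading. The lines with '.' scored 3 need the shared label and '.' present in Q6.

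**The case against.** The strongest reply is that the code may be sound for complete diaries. With the label shared across items and four Q6 answers, code 3 needs no rule because it already equals its score, and the result is an ordered 3, 2, 1, 0. This is a fair reading and cannot be excluded. It does leave the rule for code 1 without a purpose, and it does nothing for missing days.

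A second reply is that summing over missing days is a feature of all the diary totals, not of stool alone. That is true, but it does not make the stool sum right. Here 0 is also a scored answer, so an unrecorded day cannot be told from a recorded one.

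A third reply is that no stool analysis is planned, so nothing is biased. That limits the importance, but the SAP itself presents the code as defining outcomes.

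A reader might infer three stronger things:
- **Two stool categories are merged at score 2.** This needs code 2 to be a stool answer. Under the shared label it is probably a yes/no text, and the SAP does not show the Q6 answers.
- **Codes are reassigned on each diary day, so a category unused on one day shifts the rest.** The shared label carries over from day to day within a run, so the printed code does not do this. Codes could differ between separate runs, for example for pre- and post-treatment files, but the SAP does not describe such runs.
- **The treatment effect on stool form is weakened by a calculable amount.** Any such figure needs an answer set and a category mix that the document does not give.

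**Conclusion.** The point holds as a defect in the handling of missing days and in the documentation of the score. On the printed text, an unrecorded day counts as 0 whenever at least one other day is recorded, so half-completing a diary at score 1 halves the total from 14 to 7. Whether '.' is also scored 3, or two answers share score 2, depends on the Q6 texts and on how the label was carried, and cannot be determined from the SAP. The statement that 0 is a real category assumes that code 6 is a recorded Q6 answer, as the rule implies. The direction of any distortion is unknown, because it depends on which arm has more incomplete diaries and on which way the scale runs. It would be too strong to say that the score does not measure consistency. What can be said is that it is wrong for incomplete diaries and cannot be verified for complete ones. Severity is low: no listed primary or secondary outcome uses Q6.

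**What to change.** In the appendix of Stata code:

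1. List the Q6 answer texts, with one explicit ordered score for each.
2. Set '.' to empty for Q6 before encoding, as is done for Q3, Q4a, Q4b and Q5.
3. Encode all days and all diaries against one named label that holds only those texts, and score every category by rule.
4. Replace the 14-day sum with the mean over days with a recorded consistency, or the proportion of recorded days in each category.
5. Re-derive the stool outcomes from the locked data.

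The cost is a few lines of code and one re-run. No new data are needed, and the primary outcome does not change.

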To determine the effectiveness of PTNS versus sham electrical stimulation (TENS) based on changes in validated incontinence scores, patient-centred FI-related symptoms and disease-specific and generic quality of life measures from baseline (bowel diary completed over two week period prior to first intervention) to end of treatment (bowel diary completed for weeks 12 and 13)

Exploratory objectives

None

Outcome measures

Primary outcome

Change in weekly FI episodes expressed as proportion of patients achieving $\geq 50\%$ reduction in FI episodes per week. The change is measured between pre- and post-treatment bowel diaries.

The number of FI episodes per day are the sum of episodes in Q2a (rush) and Q2b (passive leakage) of the bowel diary. The average number per week is the sum of all 14 days, divided by 2.

$\%change = 100\% \times (\#FI(\text{baseline}) - \#FI(\text{end of intervention})) / \#FI(\text{baseline})$

Where #FI is the average number of episodes of FI per week. Where %change is negative, this represents an increase in FI episodes; where it is positive, this represents a decrease in FI episodes.

A patient achieving a $\geq 50\%$ reduction will be classed as a treatment success, otherwise the patient is classed as a treatment failure.

Secondary outcomes

Percentage change in FI episodes per week, from baseline (the two-week period just before the 1st treatment) to end of treatment i.e. bowel diary for two weeks after the 12th treatment; for three additional cut offs: an improvement $\geq 25\%$ vs. less, an improvement $\geq 75\%$ vs. less and an improvement of 100% vs. less

Continuous change in FI episodes per week; i.e. average number of FI episodes per week for the two weeks post-treatment, minus average number of FI episodes per week at baseline (from pre-treatment two-week bowel diary).

Continuous change in FI episodes per week (rush and passive leakage as two separate outcomes); i.e. average number of episodes per week for the two weeks post-treatment, minus average number of episodes per week at baseline (from pre-treatment two-week bowel diary).

St Mark's incontinence score (Vaizey et al. 1999)

Likert scale of patient's global impression of success

Patient-centred FI-related symptoms

Disease specific and generic quality of life measures

- EQ-5D

- SF-36 (8 domains)

- Faecal incontinence quality of life score- four domains: coping, embarrassment, lifestyle and depression

- Gastro-intestinal quality of life score

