Age, sex, history of faecal incontinence (including type), urinary symptom history, previous faecal incontinence treatments, medications, past medical history, past obstetric history. (see CRF 2 v5 for items)

Bowel diary (14 consecutive days)

Gastrointestinal quality of life index, patient centred FI symptoms, SF-36 Health Survey, QoL scale for faecal incontinence, St. Mark's faecal incontinence score, EQ-5D health questionnaire (see CRF 3 v3 for detail)

Follow up

Visits 2-13: PTNS or tens machine settings and response (sensory or motor), adverse events, any change in pad usage, any changes in medication use? (see CRF 5 v3)

Week 7: bowel diary over 7 consecutive days

Final visit (post treatment) (week 14): which treatment did patient think they were on?

Any effect on urinary symptoms? Any change in loperamide or codeine use? Any change in pad use? How patient felt before, during and after treatment, Likert scale of success.

Bowel diary over 14 consecutive days

CRF 3 v3

Timing of data collection

Event	Visit 1	Telephone Conversation	Visit 2	Visits 3-13	Visit 14
Eligibility assessment	X				
Bowel Diary		X		Visit 7-8	X
Consent			X		
Participant Contact Information Sheet			X		
Eligibility assessment (CRF1)			X		
Initial assessment (CRF2)			X		
Questionnaires (CRF3)			X		X
Randomisation			X		
Randomisation information (CRF4)			X		
Intervention			X	X	
Record stimulation parameters adverse events and medication / pad usage (CRF5)			X	X	
Adverse Events Log			X	X	X
Concomitant Medications Log			X	X	X
Post treatment Information (CRF6)					X
Final Study Visit Information (CRF7)					X

GENERAL ISSUES FOR STATISTICAL ANALYSIS

All analyses will be conducted two sided and significance interpreted at the 5% level.

Blinding of the statistical analysis

The trial statistician will remain blind to allocation until this analysis plan was signed off

Analysis populations

Intent-to-treat population

The intention-to-treat (ITT) sample is defined for this trial as all participants randomised into the trial, *who received at least their first treatment*, included in the intervention group to which they were randomised.

Available-case population

N/A

Per protocol population

Patients attending at least 10 treatment sessions in 13 weeks will be classed as treatment completers.

Safety population

N/A

Other populations

N/A

Database

Description

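### The printed primary-outcome code counts unrecorded days in a partly completed diary as zero episodes and always divides by 2, so short diaries can misclassify responders

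*SAP*

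**What the plan says.** The SAP's primary outcome definition says "The average number per week is the sum of all 14 days, divided by 2". It presumes a complete diary and gives no rule for a partial one.

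Appendix (a) implements it as follows:

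- Rush episodes are summed by a call that begins "egen uncontrolled_a = rowtotal(Q2a_1 Q2a_2 Q2a_3 Q2a_4 Q2a_5 Q2a_6" and ends "Q2a_7 Q2a_8 Q2a_9 Q2a_10 Q2a_11 Q2a_12 Q2a_13 Q2a_14), missing". Passive leakage is summed the same way.
- The two totals are added, and the weekly rate is "generate FI_epi_pw = FI_episodes/2".
- Two counters of missing days are created, "egen m_unc_a = rowmiss(Q2a_1 Q2a_2 Q2a_3 Q2a_4 Q2a_5 Q2a_6 Q2a_7" and "egen m_unc_b = rowmiss(Q2b_1 Q2b_2 Q2b_3 Q2b_4 Q2b_5 Q2b_6 Q2b_7". Both stop at day 7, and no later line uses either.
- The primary classification is "generate Responder_50 = 1 if FI_epi_pw2/FI_epi_pw0<=.5", where suffix 2 is post-treatment and suffix 0 is baseline.

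The section on amendments to version 1.0 says this code was refined during the analysis so that patients with under seven days of diary data are handled correctly, and that it replaced the earlier listing. The missing-data section sends a patient to multiple imputation when post-treatment data are unavailable. It does not mention partly completed diaries.

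**The concern.** In Stata, `rowtotal` with the `missing` option returns missing only if every listed variable is missing. Otherwise a missing day adds zero. With a fixed divisor of 2, a patient who records k of 14 days is given about k/14 of the true weekly rate. `Responder_50` is a ratio of two such rates, so a short post-treatment diary pushes the patient towards success and a short baseline diary towards failure.

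The result is non-missing, so the patient enters the analysis as observed and bypasses the imputation.

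The same rate feeds the 25%, 75% and 100% cut-offs, the continuous FI outcome and the baseline covariate. The sample size section says the main inference will be a comparison of PTNS results with those of other treatments, so absolute success rates matter as well as the difference between arms.

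The appendix handles other instruments differently. The GI quality-of-life total, the St Mark's score, the patient-centred mean and the four FI-QOL domains are each set to missing when any item is missing. The diary has counters but no line that acts on them.

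**Working it through.** **Inputs.** From the SAP: a 14-day diary, a divisor of 2, and the responder rule of post/baseline ratio ≤ 0.5 (primary outcome definition and Appendix (a)); design rates of 55% and 35% (sample size section). Assumed, because the SAP does not give them: the number of days recorded, the share of incomplete diaries, and the distribution of episode rates.

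**Threshold with a short post-treatment diary.** Take a constant daily rate, a complete baseline diary, k recorded post-treatment days and true reduction R.

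Coded ratio = (k/14) × (1 − R). The patient is a responder if this is ≤ 0.5, that is, if R ≥ 1 − 7/k.

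| Recorded post-treatment days | True reduction needed | Apparent reduction with no change, 1 − k/14 |
|---|---|---|
| 14 | 1 − 7/14 = 50% (the plan's own rule) | 0% |
| 12 | 1 − 7/12 = 42% | 14.3% |
| 10 | 1 − 7/10 = 30% | 28.6% |
| 7 | 1 − 7/7 = 0% | 50.0% |

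Example: one episode a day before and after treatment, with 7 post-treatment days recorded. Coded: 3.5/7 = 0.50, a responder with no change. Per recorded day: 7/7 = 1.00, a non-responder.

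**Short baseline diary.** With j recorded baseline days and a complete post-treatment diary, the coded ratio is (1 − R) × 14/j. A true 60% reduction with 11 baseline days gives 0.4 × 14/11 = 0.509, a failure. With 12 days it gives 0.467, a success. If both diaries are short by the same number of days, the factors cancel.

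**What stays missing.** If all 14 days are blank, or if the whole rush column or the whole passive column is blank, the sum of the two totals is missing. `Responder_50` then stays missing as well.

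**Chance variation.** Simulation with illustrative settings: baseline weekly rate gamma (mean 8, shape 0.9) plus 0.5, lognormal individual ratios (SD 0.8), Poisson counts, calibrated to 35% and 55% responders with full diaries.

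| Post-treatment days recorded | Full-diary rate | As printed | Per recorded day |
|---|---|---|---|
| 7 to 13, equally likely | 35% | 49% | 34% |
| 7 to 13, equally likely | 55% | 68% | 53% |
| exactly 7 | 35% | 63% | 37% |

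**Trial level.** If 20% of patients in each arm have 7 to 13 post-treatment days:

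- Sham: 0.8 × 35 + 0.2 × 49 = 37.8%.
- PTNS: 0.8 × 55 + 0.2 × 68 = 57.6%.
- Difference: 19.8 points against 20.

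If there is no treatment effect (35% in both arms) and 20% of one arm but 5% of the other is affected, the spurious difference is (0.20 − 0.05) × 14 = 2.1 points.

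**The case against.** **Unprinted code.** The listing is not complete, runnable code. The step that creates the baseline and post-treatment versions of the rate is not shown, and counters that nothing uses suggest a later step was left out. That is possible. But the SAP presents this listing as the replacement that handles short diaries, and it contains no such step. Either the code or the listing needs correcting.

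**A blank may mean none.** A patient with no uncontrolled movements may leave those boxes empty, and zero is then right. The SAP does not say what a blank means. This stands as an assumption of the finding, and the fix has to settle it. It also rules out a repair that calls a day recorded only when a rush or passive count is filled in. A day with controlled motions entered and the other boxes empty would then be dropped, which would inflate the rate.

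**Small effect.** A few missing days change the class only when the ratio crosses 0.5, and equal incompleteness in the two arms leaves the difference almost unchanged. Patients unable to fill in diaries are excluded, and all primary outcome data were checked by a second person. This stands as a limit on size. Those checks do not correct a rule in the derivation code.

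**Stronger readings that are not supported.**

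- A reader might infer that the 7-day mid-treatment diary ("Week 7: bowel diary over 7 consecutive days") has its rate halved. The listing does not show this code being run on that diary. A uniform halving would in any case leave a multivariate normal imputation of the other variables essentially unchanged.
- A reader might infer a serious loss of power. If 20% of all true non-responders became responders, the rates would be 64% and 48%, and power at 106 per arm would fall from 83.8% to 65.2% (formula without continuity correction). In the simulation, 14/65 = 22% of affected sham non-responders and 13/45 = 29% of affected PTNS non-responders convert. About 93% of sham and 69% of PTNS patients would then need incomplete diaries (0.20 × 65/14 and 0.20 × 45/13). Nothing in the SAP suggests that.

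**Conclusion.** The point holds for the code as printed. Partly completed diaries are scored as if unrecorded days were free of episodes, and the amendments section claims handling that the listing does not contain. For an individual patient the distortion can be large: the required true reduction falls to 42%, 30% and 0% at 12, 10 and 7 recorded post-treatment days, with the opposite error for a short baseline diary. Affected patients are analysed as observed unless a whole rush or passive column is blank.

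The size for the trial cannot be fixed from the SAP, because the share of incomplete diaries is not stated. Under the illustrative 20% in both arms, success rates rise by about 3 points each and the difference barely moves. Material bias in the treatment effect arises mainly if completeness differs by arm. A reader should not conclude that the trial's comparison is known to be wrong. The supported conclusion is that the primary outcome's derivation is faulty for short diaries and must be corrected. This rests on a blank day meaning an unrecorded day, and the threshold figures also assume a roughly constant daily rate.

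**What to change.** In Appendix (a):

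1. Count recorded days over all 14 days. A day is recorded if it has any entry for controlled motions (Q1), rush (Q2a) or passive leakage (Q2b).
2. State that a blank Q2a or Q2b counts as zero only on a recorded day.
3. Compute `FI_epi_pw` = 7 × `FI_episodes` / recorded days.
4. Set the rate to missing, and so to multiple imputation, below a stated minimum such as 7 recorded days.
5. Apply the same rule at baseline and post-treatment. Use the same formula if the code is run on the 7-day mid-treatment diary.
6. Reword the primary outcome sentence on the 14-day sum to match. Remove the two day 1 to 7 counters, or replace them with the new count.

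It would also help to report the number of recorded days by arm and time point, because the size of the problem depends on it.

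The cost is a few lines of Stata, one reworded sentence and a few more imputed patients. A rate from fewer days is also noisier: in the simulation with exactly 7 days, the corrected responder rate was 37% against 35% with full diaries. That is the reason for stating a minimum.
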